3.3.4 Confirmation Scans

Verification of Response: To be assigned a status of CR or PR, changes in tumor measurements must be confirmed by consecutive repeat assessments that should be performed no less than

28 days after the criteria for response are first met. For this study, the next scheduled tumor assessment can meet this requirement.

Verification of Progression: Progression of disease should be verified in cases where progression is equivocal. If repeat scans confirm PD, then progression should be declared using the date of the initial scan. If repeat scans do not confirm PD, then the subject is considered to not have progressive disease.

**APPENDIX 6 INTERNATIONAL METASTATIC RCC DATABASE
CONSORTIUM (IMDC) PROGNOSTIC CRITERIA**

Adverse Prognostic Factors
Clinical
KPS < 80% Time from diagnosis to treatment < 1 year
Laboratory
Hemoglobin < LLN Corrected calcium > ULN Absolute neutrophil count > ULN Platelet count > ULN

LLN = Lower limit of normal

ULN = Upper limit of normal

Corrected calcium (mg/dL) = measured total Ca (mg/dL) + 0.8 (4.0 - serum albumin [g/dL]), where 4.0 represents the average albumin level in g/dL.

Corrected calcium (mmol/L) = measured total Ca (mmol/L) + 0.02 (40 - serum albumin [g/L]), where 40 represents the average albumin level in g/L

Risk Group Based on Number of Adverse Prognostic Factors	
Number of Adverse Prognostic Factors Present	Risk Group
0	Favorable
1-2	Intermediate
3-6	Poor

Reference: Heng D, Xie W, Regan M, et al. Prognostic factors for overall survival in patients with metastatic renal cell carcinoma treated with vascular endothelial growth factor-targeted agents: results from a large, multicenter study. J Clin Oncol 2009; 27(34):5794-5799.

APPENDIX 7 PERFORMANCE STATUS SCALES

STATUS	SCALES		STATUS
	KARNOFSKY	ZUBROD-ECOG- WHO	
Normal, no complaints	100	0	Normal activity
Able to carry on normal activities Minor signs or symptoms of disease	90	0	
Normal activity with effort	80	1	Symptoms, but fully ambulatory
Cares for self. Unable to carry on normal activity or to do active work	70	1	
Requires occasional assistance, but able to care for most of his needs	60	2	Symptomatic, but in bed < 50% of the day
Requires considerable assistance and frequent medical care	50	2	
Disabled. Requires special care and assistance	40	3	Needs to be in bed > 50% of the day, but not bedridden
Severely disabled. Hospitalization indicated though death non imminent	30	3	
Very sick. Hospitalization necessary. Active supportive treatment necessary	20	4	Unable to get out of bed
Moribund	10	4	
Dead	0	5	Dead

APPENDIX 8 MANAGEMENT ALGORITHMS FOR IMMUNO-ONCOLOGY AGENTS

These general guidelines constitute guidance to the Investigator and may be supplemented by discussions with the Medical Monitor representing the Sponsor. The guidance applies to all immuno-oncology agents and regimens.

A general principle is that differential diagnoses should be diligently evaluated according to standard medical practice. Non inflammatory etiologies should be considered and appropriately treated.

[figure not shown]
Corticosteroids are a primary therapy for immuno-oncology drug-related adverse events. The oral equivalent of the recommended IV doses may be considered for ambulatory patients with low-grade toxicity. The lower bioavailability of oral corticosteroids should be taken into account when switching to the equivalent dose of oral corticosteroids.

Consultation with a medical or surgical specialist, especially prior to an invasive diagnostic or therapeutic procedure, is recommended.

The frequency and severity of the related adverse events covered by these algorithms will depend on the immuno-oncology agent or regimen being used.

GI Adverse Event Management Algorithm

Rule out non-inflammatory causes. If non-inflammatory cause is identified, treat accordingly and continue I-O therapy. Opiates/narcotics may mask symptoms of perforation. Infliximab should not be used in cases of perforation or sepsis.

[figure not shown]

Patients on IV steroids may be switched to an equivalent dose of oral corticosteroids (e.g. prednisone) at start of tapering or earlier, once sustained clinical improvement is observed. Lower bioavailability of oral corticosteroids should be taken into account when switching to the equivalent dose of oral corticosteroids.

Updated 05-Jul-2016

Renal Adverse Event Management Algorithm

Rule out non-inflammatory causes. If non-inflammatory cause, treat accordingly and continue I-O therapy

[figure not shown]

Patients on IV steroids may be switched to an equivalent dose of oral corticosteroids (e.g. prednisone) at start of tapering or earlier, once sustained clinical improvement is observed. Lower bioavailability of oral corticosteroids should be taken into account when switching to the equivalent dose of oral corticosteroids.

Updated 05-Jul-2016

Pulmonary Adverse Event Management Algorithm

Rule out non-inflammatory causes. If non-inflammatory cause, treat accordingly and continue I-O therapy. Evaluate with imaging and pulmonary consultation.

[figure not shown]

Patients on IV steroids may be switched to an equivalent dose of oral corticosteroids (e.g. prednisone) at start of tapering or earlier, once sustained clinical improvement is observed. Lower bioavailability of oral corticosteroids should be taken into account when switching to the equivalent dose of oral corticosteroids.

Updated 05-Jul-2016

Hepatic Adverse Event Management Algorithm

Rule out non-inflammatory causes. If non-inflammatory cause, treat accordingly and continue I-O therapy. Consider imaging for obstruction.

Patients on IV steroids may be switched to an equivalent dose of oral corticosteroids (e.g. prednisone) at start of tapering or earlier, once sustained clinical improvement is observed. Lower bioavailability of oral corticosteroids should be taken into account when switching to the equivalent dose of oral corticosteroids.

[figure not shown]
*I-O therapy may be delayed rather than discontinued if AST/ALT ≤ 8 x ULN or T.bili ≤ 5 x ULN.

**The recommended starting dose for grade 4 hepatitis is 2 mg/kg/day methylprednisolone IV.

Updated 05-Jul-2016

Endocrinopathy Management Algorithm

Rule out non-inflammatory causes. If non-inflammatory cause, treat accordingly and continue I-O therapy. Consider visual field testing, endocrinology consultation, and imaging.

[figure not shown]

Patients on IV steroids may be switched to an equivalent dose of oral corticosteroids (e.g. prednisone) at start of tapering or earlier, once sustained clinical improvement is observed. Lower bioavailability of oral corticosteroids should be taken into account when switching to the equivalent dose of oral corticosteroids.

Updated 05-Jul-2016

Skin Adverse Event Management Algorithm

Rule out non-inflammatory causes. If non-inflammatory cause, treat accordingly and continue I-O therapy.

Patients on IV steroids may be switched to an equivalent dose of oral corticosteroids (e.g. prednisone) at start of tapering or earlier, once sustained clinical improvement is observed. Lower bioavailability of oral corticosteroids should be taken into account when switching to the equivalent dose of oral corticosteroids.

[figure not shown]
*Refer to NCI CTCAE v4 for term-specific grading criteria.

^If SJS/TEN is suspected, withhold I-O therapy and refer patient for specialized care for assessment and treatment. If SJS or TEN is diagnosed, permanently discontinue I-O therapy.

Updated 05-Jul-2016

Neurological Adverse Event Management Algorithm

Rule out non-inflammatory causes. If non-inflammatory cause, treat accordingly and continue I-O therapy.

Patients on IV steroids may be switched to an equivalent dose of oral corticosteroids (e.g. prednisone) at start of tapering or earlier, once sustained clinical improvement is observed. Lower bioavailability of oral corticosteroids should be taken into account when switching to the equivalent dose of oral corticosteroids.

Updated 05-Jul-2016

Myotoxicity (Myositis, Myocarditis, Rhabdomyolysis) Adverse Event Management Algorithm
 
Rule out non-inflammatory causes. If non-inflammatory, cause, treat accordingly and continue I-O therapy.
		
Grade of Myotoxicity*	Management	Follow UP

Grade 1: Asymptomatic with laboratory or cardiac imaging abnormalities (myocarditis)
 
Mild pain (myositis)
	
 • Consider delay of I-O therapy • Monitor CPK and troponin and emergence of new symptoms; EKG • Cardiology consultation for abnormal cardiac labs/imaging • Consider steroids (up to 2 mg/kg/day methylprednisolone IV or oral equivalent) • Symptomatic therapy (myositis) 	
 • Close monitoring for new or worsening symptoms • If worsens: Treat as Grade 2 or 3/4

Grade 2: Symptoms with mild to moderate activity or exertion (myocarditis) Moderate pain associated with weakness; pain limiting instrumental activities of daily living (myositis)
	
 • Delay I-O therapy; consider hospitalization • Rule out alternative causes (myocardial ischemia, viral infection, nutritional deficiency, thyroid, etc) • Prompt cardiology consultation for any cardiac signs and/or symptoms, evaluation may include: 
 • EKG ± continuous cardiac monitoring • Echocardiogram • Troponin and CPK monitoring • In absence of cardiac signs and/or symptoms: 
 • Monitor CPK and renal function • Consider EKG and troponin monitoring • Up to 2 mg/kg/day methylprednisolone IV or oral equivalent • Consider prophylactic antibiotics for opportunistic infections 	
 • If improves to grade 1 or baseline, taper steroids after cardiac symptoms resolve over at least 1 month • Retreatment may be considered after resolution to baseline and completion of steroid taper • If no improvement observed, treat as Grade 3-4


Grade 3: Severe with symptoms at rest or with minimal activity or exertion (myocarditis)
 
Pain associated with severe weakness; limiting self care activities of daily living (myositis)
 
Grade 4: Life Threatening; urgent intervention indicated (e.g., continuous IV therapy or mechanical hemodynamic support)
	
 • Permanently discontinue I-O therapy; hospitalize • Rule out alternative causes (myocardial ischemia, viral infection, nutritional deficiency, thyroid, etc) • Urgent cardiology consultation for any cardiac signs and/or symptoms, evaluation may include: 
 • EKG ± continuous cardiac monitoring • Echocardiogram • Troponin and CPK monitoring • Consider Cardiac MRI and myocardial biopsy • In absence of cardiac signs and/or symptoms: 
 • Monitor CPK and renal function • Consider EKG and troponin monitoring • 2-4 mg/kg/day methylprednisolone IV or 1 g IV bolus • Add prophylactic antibiotics for opportunistic infections 	
 • If improves to grade 1 or baseline, taper steroids over at least 6 weeks • If no improvement, consider additional immunosuppressants
---	---	---

*Patients with clinical signs or symptoms of rhabdomyolysis should be evaluated for myositis/myocarditis per the recommendations in this algorithm.

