7.4 Dosage Modification

7.4.1 Dose Delay Criteria

Regardless of whether or not the event is attributed to nivolumab, ipilimumab, or BMS-986237, all study treatments must be delayed until treatment can resume. Tumor assessments for all participants should continue as per protocol even if dosing is delayed.

Nivolumab, ipilimumab, and BMS-986237 administration should be delayed for the following:

- Grade 2 non-skin, drug-related adverse event, with the exception of fatigue
- Grade 2 drug-related creatinine, AST, ALT and/or Total Bilirubin abnormalities
- Grade 3 skin, drug-related adverse event
- Grade 3 drug-related laboratory abnormality, with the following exceptions:
 - Grade 3 lymphopenia or asymptomatic amylase or lipase does not require dose delay
 - Grade ≥ 3 AST, ALT, Total Bilirubin will require dose discontinuation (see [Section 7.4.3](#))
- Any adverse event, laboratory abnormality, or intercurrent illness which, in the judgment of the investigator, warrants delaying the dose of study medication.

Participants who require delay of study treatment should be re-evaluated weekly or more frequently if clinically indicated and resume study treatment dosing when re-treatment criteria are met.

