7.4.2 Criteria to Resume Treatment

Participants may resume treatment with study treatment when the drug-related AE(s) resolve to Grade \leq 1 or baseline value, with the following exceptions:

- Participants may resume treatment in the presence of Grade 2 fatigue
- Participants who have not experienced a Grade 3 drug-related skin AE may resume treatment in the presence of Grade 2 skin toxicity
- For participants with Grade 2 AST, ALT and/or Total Bilirubin abnormalities, dosing may resume when laboratory values return to baseline and management with corticosteroids, if needed, is complete.
- Participants with combined Grade 2 AST/ALT AND total bilirubin values meeting discontinuation parameters (Section 7.4.3) should have treatment permanently discontinued.
- Drug-related pulmonary toxicity, diarrhea or colitis or myocarditis myositis, rhabdomyolysis must have resolved to baseline before treatment is resumed. Participants with persistent Grade 1 pneumonitis after completion of a steroid taper over at least 1 month may be eligible for retreatment if discussed with and approved by BMS Medical Monitor.

Participants with drug-related endocrinopathies adequately controlled with only physiologic hormone replacement may resume treatment after consultation with the BMS Medical Monitor. Adrenal insufficiency requires discontinuation regardless of control with hormone replacement.

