7.4.3 Dose Discontinuation

The assessment for discontinuation of nivolumab should be made separately from the assessment made for discontinuation of ipilimumab. Although there is overlap among the discontinuation criteria, if discontinuation criteria are met for ipilimumab but not for nivolumab, treatment with nivolumab may continue if ipilimumab is discontinued. In this instance, the patient would be considered off part 1 of the study and must have a 6 weeks interval before moving on to part 2 of the study (nivolumab monotherapy).

If a participant in any of the nivolumab/ipilimumab combination arms meets criteria for discontinuation and investigator is unable to determine whether the event is related to both or one study drug, the participant should discontinue both nivolumab and ipilimumab and be taken off the treatment phase of the study.

Study treatment should be permanently discontinued for the following:

- Any Grade 2 drug-related uveitis, eye pain or blurred vision that does not respond to topical therapy and does not improve to Grade 1 severity within the re-treatment period OR requires systemic treatment
- Any Grade 3 non-skin, drug-related adverse event lasting $>$ 7 days, or recurs with the following exceptions for laboratory abnormalities, diarrhea, colitis, neurologic toxicity, drug-related

uveitis, pneumonitis, bronchospasm, myositis, myocarditis, rhabdomyolysis, hypersensitivity reactions, infusion reactions, and endocrinopathies:

- Grade 3 drug-related, diarrhea, colitis, neurologic toxicity, uveitis, pneumonitis, bronchospasm, myositis, myocarditis, rhabdomyolysis, hypersensitivity reaction, or infusion reaction of any duration requires discontinuation
- Grade 3 drug-related endocrinopathies, adequately controlled with only physiologic hormone replacement do not require discontinuation. Adrenal insufficiency requires discontinuation regardless of control with hormone replacement.
- Grade 3 drug-related laboratory abnormalities do not require treatment discontinuation except:
 - ◆ Grade 3 drug-related thrombocytopenia > 7 days or associated with bleeding requires discontinuation
 - ◆ Any drug-related liver function test (LFT) abnormality that meets the following criteria requires discontinuation:
 - Grade \geq 3 drug-related AST, ALT or Total Bilirubin requires discontinuation*
 - Concurrent AST or ALT > 3 x ULN and total bilirubin > 2x ULN

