* In most cases of Grade 3 AST or ALT elevation, study treatment(s) will be permanently discontinued. If the investigator determines a possible favorable benefit/risk ratio that warrants continuation of study treatment(s), a discussion between the investigator and the BMS Medical Monitor/designee must occur.

- Any Grade 4 drug-related adverse event or laboratory abnormality (including but not limited to creatinine, AST, ALT, or Total Bilirubin).
- Any event that leads to delay in dosing lasting > 6 weeks from the previous dose requires discontinuation, with the following exceptions:
 - Dosing delays to allow for prolonged steroid tapers to manage drug-related adverse events are allowed. However, dosing must be discontinued for any drug related AE that requires treatment with 10mg/day or greater prednisone or equivalent for more than 12 weeks.
 - Dosing delays lasting > 6 weeks from the previous dose that occur for non-drug-related reasons may be allowed if approved by the BMS Medical Monitor.

Prior to re-initiating treatment in a participant with a dosing delay of >6 weeks, the BMS Medical Monitor must be consulted. Tumor assessments should continue as per protocol even if dosing is delayed. Periodic study visits to assess safety and laboratory studies should also continue every 6 weeks or more frequently if clinically indicated during such dosing delays.

Any adverse event, laboratory abnormality, or intercurrent illness which, in the judgment of the Investigator, presents a substantial clinical risk to the participant with continued nivolumab dosing.

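### The Appendix 8 hepatic note permits delay at combined liver values for which Protocol Sections 7.4.2 and 7.4.3 require permanent discontinuation, and no text says which prevails

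*Protocol*

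**What the plan says.** Four places in the protocol bear on stopping treatment for abnormal liver tests.

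- **Section 7.4.1 (Dose Delay Criteria)** excepts Grade 3 or higher liver tests from the delay rule: "AST, ALT, Total Bilirubin will require dose discontinuation". It points to 7.4.3 and states no combined threshold.
- **Section 7.4.2 (Criteria to Resume Treatment)** addresses "Participants with combined Grade 2 AST/ALT AND total bilirubin values meeting discontinuation parameters" and directs permanent discontinuation, with a reference to 7.4.3.
- **Section 7.4.3 (Dose Discontinuation)** has two drug-related liver criteria. The first covers Grade 3 or higher single tests, "drug-related AST, ALT or Total Bilirubin requires discontinuation", and carries an asterisk. The second, "Concurrent AST or ALT > 3 x ULN and total bilirubin > 2x ULN", carries none. The asterisked footnote begins: "In most cases of Grade 3 AST or ALT elevation, study treatment(s) will be permanently discontinued". It goes on to say that if the investigator sees a favourable benefit/risk balance for continuing, "a discussion between the investigator and the BMS Medical Monitor/designee must occur".
- **Appendix 8, hepatic algorithm**, has a note under a figure that is not shown: "I-O therapy may be delayed rather than discontinued if AST/ALT ≤ 8 x ULN or T.bili ≤ 5 x ULN". The visible note mentions no contact with the Medical Monitor.

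Appendix 8 introduces its algorithms as guidance for the investigator that applies to all immuno-oncology agents and regimens. Section 7.4.4 sends investigators to it for help in assessing and managing these events. Neither place says whether Section 7.4 or the appendix prevails when they differ.

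**The concern.** The appendix note and the combined criterion in 7.4.3 both apply to AST/ALT and bilirubin expressed as multiples of ULN, and they lead to different actions over the same range. An investigator who opens the algorithm, as Section 7.4.4 invites, finds an option to delay. An investigator who opens 7.4.3 finds a mandatory stop.

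Participant safety is at stake first. The same two limits, above 3 x and above 2 x ULN, form the laboratory part of the potential drug-induced liver injury definition in Section 9.2.7, which must be reported as an SAE when its other conditions are met. One laboratory pattern could therefore be a mandatory stop, a reportable event and a permitted delay.

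The data are affected second. A stop or delay decision can change how many Part 1 infusions a participant receives. That changes the number of two-day windows in which a primary-endpoint event can occur, the date that starts the 30-day window for the Grade 3-5 AE endpoints, and the discontinuation tables in SAP Section 7.3.1. The study is open-label and Section 5.1.1 gives no data monitoring committee, so uniform conduct depends on the written rules.

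**Working it through.** There is no stated figure to reproduce. The check compares the two rules as logical conditions. Let A be AST or ALT and B be total bilirubin, both as multiples of ULN and both judged drug-related.

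**Inputs**

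- Section 7.4.3, combined criterion: discontinue if A > 3 and B > 2.
- Appendix 8 note, literal reading: delay permitted if A ≤ 8 or B ≤ 5.
- Appendix 8 note, narrow reading: delay permitted if A ≤ 8 and B ≤ 5.

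**Step 1: where the rules overlap**

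- Narrow reading: (A > 3 and B > 2) together with (A ≤ 8 and B ≤ 5) gives 3 < A ≤ 8 and 2 < B ≤ 5.
- Literal reading: all pairs with A > 3 and B > 2, except those with both A > 8 and B > 5.

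The narrow region lies wholly inside the literal one, so it is in conflict whichever way the note is read.

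**Step 2: pairs put through both rules**

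| A | B | 7.4.3 combined rule | Note, 'or' | Note, 'and' | Conflict |
|---|---|---|---|---|---|
| 4 | 2.5 | stop | delay permitted | delay permitted | both readings |
| 6 | 3 | stop | delay permitted | delay permitted | both readings |
| 8 | 5 | stop | delay permitted | delay permitted | both readings |
| 12 | 4 | stop | delay permitted | no | 'or' only |
| 30 | 4 | stop | delay permitted | no | 'or' only |
| 9 | 6 | stop | no | no | none |
| 3 | 2 | not triggered | delay permitted | delay permitted | none |
| 8 | 1 | not triggered | delay permitted | delay permitted | none |
| 1 | 5 | not triggered | delay permitted | delay permitted | none |

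The last three rows concern the combined rule only. Single-test criteria are taken next.

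**Step 3: isolated elevations**

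7.4.1 and 7.4.3 word the single-test rule by CTCAE grade, and the documents give no cut-off in multiples of ULN. The width of any overlap therefore rests on an assumed start of Grade 3.

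- AST/ALT: overlap = 8 − assumed start. A start at 4 gives 8 − 4 = 4 x ULN. A start at 8 gives 0.
- Bilirubin: overlap = 5 − assumed start. A start at 2 gives 5 − 2 = 3 x ULN. A start at 5 gives 0.

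For AST/ALT the 7.4.3 footnote already allows continuation after a Medical Monitor discussion. What remains there is mainly that the visible appendix note omits that step. For bilirubin there is a conflict only if Grade 3 is assumed to begin below 5 x ULN.

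**Step 4: does the 7.4.3 footnote remove the combined conflict?**

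The asterisk is on the Grade 3 or higher line, not on the combined line, and the footnote's first sentence speaks of Grade 3 AST or ALT. Nothing in it refers to concurrent elevations, and 7.4.2 restates permanent discontinuation for them. The combined conflict stands.

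**The case against.** The strongest reply is that the two texts do not carry equal weight. Appendix 8 is general guidance across agents, and its hepatic page was last updated on 05-Jul-2016, before the original protocol of 25-Oct-2016. Its note is permissive, whereas 7.4.2 and 7.4.3 are study-specific and directive. A site that stops at A = 6 and B = 3 complies with every passage; a site that delays departs from 7.4.2 and 7.4.3. A reader might infer that sites can act in opposite ways with equal support from the protocol. The documents do not support that, and this part of the reply stands. It does not dispose of the point, because the ranking has to be inferred and 7.4.4 refers sites to the appendix without one.

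Second, the note's asterisk belongs to a figure that is not shown. Which row it qualifies, and whether the figure has its own rule for combined values, cannot be checked. That limit stands. The note's own wording does show that it stands in place of an instruction to discontinue.

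Third, there are safeguards. Section 9 requires immediate safety concerns to be discussed with the sponsor to decide whether treatment continues, and potential liver injury must be reported as an SAE. These make unnoticed divergence less likely but leave the wording as it is.

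Fourth, no liver term appears in the primary-endpoint term list. Any effect on that endpoint is indirect, through the number of infusions, and no figure can be put on it.

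**Conclusion.** The contradiction is real and confined. On the visible text it covers 3 < AST/ALT ≤ 8 x ULN with 2 < bilirubin ≤ 5 x ULN, under either reading of the note and without any outside cut-off. It rests on the note applying to combined values as its words suggest, which the missing figure prevents us from confirming. The number of participants who would fall in this range is not in the documents.

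Four stronger readings are tempting and are not supported:

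- **That 7.4.1 also sets a combined threshold.** It gives only the Grade 3 or higher rule and refers to 7.4.3.
- **That isolated Grade 3 or higher bilirubin is contradictory outright.** This needs an assumed start of Grade 3 below 5 x ULN.
- **That the 7.4.3 footnote plainly excludes bilirubin.** Its first sentence names only AST and ALT. Its asterisk, however, is on a line that includes bilirubin, and its second sentence is not tied to any one test.
- **That the note was meant to allow delay at any AST/ALT provided bilirubin is at most 5 x ULN.** The literal 'or' has that effect, as at A = 30 and B = 4, but the visible text does not show that this was intended.

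This is an internal inconsistency in a stopping rule for a serious toxicity and should be corrected.

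**What to change.** Reconcile the Appendix 8 hepatic note with Sections 7.4.1, 7.4.2 and 7.4.3, including the 7.4.3 footnote, or add a statement of which text prevails in this study when they differ. The reconciled text should make three things clear:

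- what applies when AST/ALT and bilirubin are raised together;
- whether the Medical Monitor discussion in the 7.4.3 footnote also applies when the appendix note is used, and to which tests;
- whether the note's 'or' is meant literally.

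Which thresholds and actions apply is for the sponsor's clinical team, and no value is proposed here. A precedence statement is about one sentence in the protocol. No change to the sample size or the analysis methods is needed.
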